4.2.9. Radiation Therapy Treatment Interruptions

Treatment interruptions are strongly discouraged. Treatment breaks must be clearly indicated in the treatment record when they occur. Patients who have treatment interruptions in radiation for >3 weeks will be taken off study. The interruption of radiation therapy for grade 4 mucositis / dermatitis / dysphagia is at the discretion of the treating radiation oncologist. Treatment breaks, if necessary, ideally should not exceed five treatment days at a time and ten treatment days total. Treatment breaks should be allowed only for resolution of severe acute toxicity and/or for intercurrent illness and not for social or logistical reasons.

4.3. NIVOLUMAB ADMINISTRATION:

4.3.1. Administration of Nivolumab

4.3.1. Administration of Nivolumab

Nivolumab will be administered at a fixed dose of 240 mg over 30-60 minutes IV two weeks prior to the beginning of RT and every 2 weeks during radiotherapy for a total of 5 doses. Then Nivolumab will be given at 480 mg over 30-60 minutes IV every 4 weeks for 10 additional doses after radiotherapy. The first dose will be given two weeks prior to the first fraction of radiation (+/- 5 days), and continued every 2 weeks (+/- 3 days). Nivolumab will thus be given in at -2 weeks, then week 0, 2, 4 and 6. Adjuvant nivolumab will then be given for a total of 10 additional doses after the completion of radiotherapy every 4 weeks (+/- 7 days).

There are no premedications for nivolumab recommended.

Doses of nivolumab may be interrupted, delayed, or discontinued depending on how well the subject tolerates the treatment.

4.3.2. Dose delay criteria apply for all drug-related AEs

Treatment delay up to 6 weeks for nivolumab from the last dose are allowable (any dose delays greater than these will require approval from the local principal investigator).

Tumor assessments for all subjects should continue as per protocol even if dosing is delayed.

Nivolumab should be delayed for the following:

- Any Grade \geq 2 non-skin, drug-related adverse event, except for fatigue and laboratory abnormalities
- Any Grade \geq 3 skin drug-related AE
- Any Grade \geq 3 drug-related laboratory abnormality with the following exceptions for lymphopenia, aspartate aminotransferase (AST), alanine aminotransferase (ALT), or total bilirubin or asymptomatic amylase or lipase:
 - Grade 3 lymphopenia does not require a dose delay
 - If a subject has a baseline AST, ALT, or total bilirubin that is within normal limits, delay dosing for drug-related Grade 2 toxicity
 - If a subject has baseline AST, ALT, or total bilirubin within the Grade 1 toxicity range, delay dosing for drug-related Grade \geq 3 toxicity
 - Any Grade \geq 3 drug-related amylase or lipase abnormality that is not associated with symptoms or clinical manifestations of pancreatitis does not require dose delay. The local principal investigator should be consulted for such Grade \geq 3 amylase or lipase abnormalities.
- Any AE, laboratory abnormality or inter-current illness which, in the judgment of the investigator, warrants delaying the dose of study medication.
- **NOTE:** Grade 3 dysphagia, dehydration, mucositis and pain are routinely encountered during reirradiation and will not require a delay in Nivolumab administration.

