4.3.3. Nivolumab Dose Discontinuation Due to Drug-Related AE(s)

Treatment with nivolumab should be permanently discontinued for any of the following:

- Any Grade 2 drug-related uveitis or eye pain or blurred vision that does not respond to topical therapy and does not improve to Grade 1 severity within the re-treatment period OR requires systemic treatment
- Any Grade 3 drug-related bronchospasm, hypersensitivity reaction, or infusion reaction, regardless of duration
- Any Grade 3 non-skin, drug-related adverse event lasting $>$ 7 days, with the following exceptions for uveitis, pneumonitis, bronchospasm, diarrhea, colitis, neurologic toxicity, hypersensitivity reaction, or infusion reaction of any duration requires discontinuation.
- Any Grade 3 neurologic toxicity including encephalitis required discontinuation of Nivolumab.
- Any Grade 3 drug-related endocrinopathies adequately controlled with only physiologic hormone replacement do not require discontinuation.

- Any Grade 3 drug-related laboratory abnormalities do not require treatment discontinuation except:
 - Grade 3 drug-related thrombocytopenia > 7 days or associated with bleeding requires discontinuation.
 - Any drug-related liver function test (LFT) abnormality that meets the following criteria require discontinuation
 - AST or ALT > 5 -10x ULN for > 2 weeks
 - AST or ALT > 10x ULN
 - Total bilirubin > 5 x ULN
 - Concurrent AST or ALT > 3 x ULN and total bilirubin > 2 x ULN
- Any Grade 4 drug-related adverse event or laboratory abnormality, except for the following events, which do not require discontinuation:
 - Grade 4 neutropenia \leq 7 days
 - Grade 4 lymphopenia or leukopenia
 - Isolated Grade 4 amylase or lipase abnormalities that are not associated with symptoms or clinical manifestations of pancreatitis and decrease to < Grade 4 within 1 week of onset. The local principal investigator should be consulted for Grade 4 amylase or lipase abnormalities
 - Isolated Grade 4 electrolyte imbalances/abnormalities that are not associated with clinical sequelae and are corrected with supplementation/appropriate management within 72 hours of their onset
- Any adverse event, laboratory abnormality, or intercurrent illness which, in the judgment of the Investigator, presents a substantial clinical risk to the subject with continued nivolumab dosing.

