4.3.4. Criteria to Resume Nivolumab Dosing

Subjects may resume treatment with nivolumab when the drug-related AE(s) resolve(s) to Grade \leq 1 or baseline, with the following exceptions:

- Subjects may resume treatment in the presence of Grade 2 fatigue.
- Subjects who have not experienced a Grade 3 drug-related skin AE may resume treatment in the presence of Grade 2 skin toxicity.
- Subjects with combined Grade 2 AST/ALT and total bilirubin values meeting discontinuation parameters should have treatment permanently discontinued.
- Drug-related pulmonary toxicity, diarrhea, or colitis must have resolved to baseline before treatment is resumed. Subjects with persistent Grade 1 pneumonitis after completion of a steroid taper over at least 1 month may be eligible for retreatment if discussed with and approved by the local principal investigator.
 - Subjects who received systemic corticosteroids for management of any drug-related toxicity must be off corticosteroids or have tapered down to an equivalent dose of prednisone \leq 10 mg/day.
- Drug-related endocrinopathies adequately controlled with only physiologic hormone replacement may resume treatment.
- Dose delay of nivolumab which results in treatment interruption of > 6 weeks requires treatment discontinuation, with exceptions as noted above.

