4.5. ENDPOINTS OF SAFETY

Safety of nivolumab will be evaluated as indicated by intensity and incidence of adverse events, graded according to US NCI CTCAE Version 4.03. Safety endpoints include:

- Events leading to dose holding
- Events leading to permanent treatment discontinuation
- The overall incidence and CTC criteria grade of adverse events, as well as relatedness of adverse events to treatment
- Causes of death

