5.4. CAUSAL RELATIONSHIP OF ADVERSE EVENT

The causal relationship to study drug is determined by a physician and should be used to assess all adverse events (AE). The causal relationship can be one of the following:

Related: There is a reasonable causal relationship between study drug administration and the AE.

Not related: There is not a reasonable causal relationship between study drug administration and the AE.

The term "reasonable causal relationship" means there is evidence to suggest a causal relationship.

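### For drug-related dysphagia, dehydration, mucositis or pain, the nivolumab rules conflict: delay at Grade 2, no delay at Grade 3, permanent stop if Grade 3 exceeds 7 days

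*Combined protocol and SAP*

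**What the plan says.** Three adjoining sections of the combined protocol and SAP govern nivolumab when toxicity occurs.

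- **Section 4.3.2 (delay).** The dose is delayed for any Grade 2 or higher "non-skin, drug-related adverse event, except for fatigue and laboratory abnormalities". A separate bullet allows a delay for any adverse event, drug-related or not, that the investigator thinks warrants it. A closing NOTE reads: "Grade 3 dysphagia, dehydration, mucositis and pain are routinely encountered during reirradiation and will not require a delay in Nivolumab administration".
- **Section 4.3.3 (permanent discontinuation).** One trigger is "Any Grade 3 non-skin, drug-related adverse event lasting" more than 7 days. The attached list reads "7 days, with the following exceptions for uveitis, pneumonitis, bronchospasm, diarrhea, colitis, neurologic toxicity, hypersensitivity reaction, or infusion reaction of any duration requires discontinuation". A further trigger is "Any Grade 4 drug-related adverse event or laboratory abnormality, except for the following events, which do not require discontinuation"; the events listed there are blood counts, amylase or lipase, and electrolytes.
- **Section 4.3.4 (resumption).** "Subjects may resume treatment with nivolumab when the drug-related AE(s) resolve(s) to Grade" 1 or lower, or baseline. Grade 2 fatigue and some Grade 2 skin toxicity are excepted.

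Attribution is set in section 5.4, which offers two categories, related and not related to study drug: "Related: There is a reasonable causal relationship between study drug administration and the AE". Section 4.5 lists dose holds among the safety endpoints, together with "Events leading to permanent treatment discontinuation".

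**The concern.** The NOTE recognises four toxicities as expected in this setting and lets nivolumab continue through them. It mentions neither Grade 2 nor permanent discontinuation, and neither section 4.3.3 nor section 4.3.4 has a matching exception. For an event judged drug-related, the milder grade is held, the more severe grade is not, and the more severe grade ends the drug if it persists beyond 7 days.

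At stake is whether a patient stays on the drug under study. Two of the section 4.5 endpoints count holds and permanent discontinuations. With three sites and no single rule, those counts would partly reflect how each site read the text. The trial has a single arm, so no comparison group would show how much of the count comes from that.

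**Working it through.** The plan states no figure on this point, so the check is a reading of the rules by grade, followed by simple arithmetic on timing and dose.

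**1. Literal outcome for one of the four toxicities, judged related to nivolumab**

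| Event | Governing text | Action |
|---|---|---|
| Grade 2 | 4.3.2 general rule; NOTE silent | Delay |
| Grade 3, up to 7 days | 4.3.2 NOTE | No delay |
| Grade 3, more than 7 days | 4.3.3; no exception | Permanent discontinuation |
| Grade 4 | 4.3.3; no exception | Permanent discontinuation |

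The list attached to the 7-day rule does not help. Its events are treated more strictly (discontinuation at any duration), and the four toxicities are not among them. The later Grade 3 carve-outs concern endocrinopathies and laboratory abnormalities.

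The reversal also runs the other way. A Grade 3 event that improves to Grade 2 within 7 days moves from no delay to delay. Section 4.3.4 then requires Grade 1 or baseline before the next dose.

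**2. The same event attributed to radiation alone**

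The answer under section 5.4 is not related. The drug-related triggers in 4.3.2 and 4.3.3 do not apply, and only the investigator-judgment bullets remain. There is no conflict.

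**3. Mixed cause**

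The section 5.4 definition of related does not require nivolumab to be the only cause. An event reasonably linked to both treatments is therefore related, and step 1 applies.

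**4. What the NOTE protects if the 7-day rule also applies**

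Doses before and during radiation are 14 days apart (section 4.3.1). Let a persisting Grade 3 event start d days after a dose. Its duration at the next dose is 14 − d days, which exceeds 7 whenever d < 7.

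- d = 3: 14 − 3 = 11 days, so 4.3.3 is met before the next dose and the NOTE protects nothing.
- d = 10: 14 − 10 = 4 days, so the NOTE protects that dose. By the following dose the duration is 28 − 10 = 18 days, and 4.3.3 has been met.

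If the ±3-day windows on two consecutive doses are both used to shorten the gap, it is 14 − 6 = 8 days, still more than 7. Read together, the two rules let the NOTE protect at most one dose per persisting event.

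**5. Size for one constructed patient**

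- Planned exposure: 5 × 240 + 10 × 480 = 1,200 + 4,800 = 6,000 mg.
- Assume a drug-related Grade 3 event that starts soon after the week 4 dose and lasts more than 7 days, with nivolumab stopped before week 6. Doses given: weeks −2, 0, 2 and 4, so 4 × 240 = 960 mg.
- Share of plan: 960 / 6,000 = 16%. Doses lost: 15 − 4 = 11.
- If the NOTE alone is followed, this event costs no doses.

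**The case against.** The strongest reply is that the NOTE was written for radiation effects. The reason it gives is reirradiation, and it follows directly after the bullet allowing a delay for any adverse event. On that reading it tells investigators not to use that discretion for expected radiation toxicity, and the drug-related triggers never arise. This stands as a plausible purpose. A reader might infer that the NOTE can only operate on events already called drug-related; that bullet shows otherwise. But the NOTE does not limit itself to unrelated events, and it sits in a section whose heading covers drug-related events. Events judged related or of mixed cause remain in conflict.

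Other replies carry part of their weight:

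- *Waiving Grade 3 implies waiving Grade 2.* This is a natural inference, but it is not written, and it leaves the 7-day rule untouched.
- *Escalation by duration is not a contradiction.* Correct in principle: the NOTE and the 7-day rule can be applied in sequence. Step 4 shows how little of the NOTE then survives, and the text does not say that this was intended.
- *The resumption rule is not a separate conflict.* Correct. An event that causes no delay leaves nothing to resume, so section 4.3.4 matters only once a dose has been held.
- *A separate radiation attribution field is needed.* A reader might infer this from section 5.4. The documents do not require it, because the not-related category already covers radiation-only events.
- *Weekly meetings can align sites.* Section 9.5.3 does provide weekly meetings and teleconferences, with toxicities on the teleconference agenda. They could limit divergence, but they do not replace a written rule.

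**Conclusion.** The conflict is real for the four named toxicities when they are judged related to nivolumab, including mixed cause. Over the course of one event, sites following the text could hold, continue or permanently stop the drug. The constructed case gives the possible size for one patient: 16% of planned exposure received against no doses lost. It rests on the assumed onset, duration and attribution.

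The documents do not support going further. A reader might infer that the conflict governs exposure in a typical patient, because the NOTE calls these toxicities routine. It calls them routine in reirradiation; nothing says how often they would be attributed to nivolumab. Nor can a patient count be given, since it would need the joint frequency of Grade 3, drug-related and longer than 7 days, which appears nowhere. The sample size and the Kaplan-Meier method for the primary endpoint are unaffected. What is affected is drug exposure and the interpretation of the two section 4.5 endpoints.

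**What to change.** Reconcile sections 4.3.2 and 4.3.3 for dysphagia, dehydration, mucositis and pain, and section 4.3.4 for the case where a dose has been held. The text should state:

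- whether the NOTE covers only events judged not related to nivolumab, or also related and mixed-cause events;
- whether it extends to Grade 2;
- whether it extends to the rule on Grade 3 events lasting more than 7 days;
- if a dose is held for one of these events, whether the general resumption criterion applies.

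Which clinical rule to adopt is for the sponsor and investigators. The cost is a short amendment to adjoining sections, with no extra visits, patients or analyses.

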4.3.3. Nivolumab Dose Discontinuation Due to Drug-Related AE(s)

Treatment with nivolumab should be permanently discontinued for any of the following:

- Any Grade 2 drug-related uveitis or eye pain or blurred vision that does not respond to topical therapy and does not improve to Grade 1 severity within the re-treatment period OR requires systemic treatment
- Any Grade 3 drug-related bronchospasm, hypersensitivity reaction, or infusion reaction, regardless of duration
- Any Grade 3 non-skin, drug-related adverse event lasting $>$ 7 days, with the following exceptions for uveitis, pneumonitis, bronchospasm, diarrhea, colitis, neurologic toxicity, hypersensitivity reaction, or infusion reaction of any duration requires discontinuation.
- Any Grade 3 neurologic toxicity including encephalitis required discontinuation of Nivolumab.
- Any Grade 3 drug-related endocrinopathies adequately controlled with only physiologic hormone replacement do not require discontinuation.

- Any Grade 3 drug-related laboratory abnormalities do not require treatment discontinuation except:
 - Grade 3 drug-related thrombocytopenia > 7 days or associated with bleeding requires discontinuation.
 - Any drug-related liver function test (LFT) abnormality that meets the following criteria require discontinuation
 - AST or ALT > 5 -10x ULN for > 2 weeks
 - AST or ALT > 10x ULN
 - Total bilirubin > 5 x ULN
 - Concurrent AST or ALT > 3 x ULN and total bilirubin > 2 x ULN
- Any Grade 4 drug-related adverse event or laboratory abnormality, except for the following events, which do not require discontinuation:
 - Grade 4 neutropenia \leq 7 days
 - Grade 4 lymphopenia or leukopenia
 - Isolated Grade 4 amylase or lipase abnormalities that are not associated with symptoms or clinical manifestations of pancreatitis and decrease to < Grade 4 within 1 week of onset. The local principal investigator should be consulted for Grade 4 amylase or lipase abnormalities
 - Isolated Grade 4 electrolyte imbalances/abnormalities that are not associated with clinical sequelae and are corrected with supplementation/appropriate management within 72 hours of their onset
- Any adverse event, laboratory abnormality, or intercurrent illness which, in the judgment of the Investigator, presents a substantial clinical risk to the subject with continued nivolumab dosing.

4.3.4. Criteria to Resume Nivolumab Dosing

Subjects may resume treatment with nivolumab when the drug-related AE(s) resolve(s) to Grade \leq 1 or baseline, with the following exceptions:

- Subjects may resume treatment in the presence of Grade 2 fatigue.
- Subjects who have not experienced a Grade 3 drug-related skin AE may resume treatment in the presence of Grade 2 skin toxicity.
- Subjects with combined Grade 2 AST/ALT and total bilirubin values meeting discontinuation parameters should have treatment permanently discontinued.
- Drug-related pulmonary toxicity, diarrhea, or colitis must have resolved to baseline before treatment is resumed. Subjects with persistent Grade 1 pneumonitis after completion of a steroid taper over at least 1 month may be eligible for retreatment if discussed with and approved by the local principal investigator.
 - Subjects who received systemic corticosteroids for management of any drug-related toxicity must be off corticosteroids or have tapered down to an equivalent dose of prednisone \leq 10 mg/day.
- Drug-related endocrinopathies adequately controlled with only physiologic hormone replacement may resume treatment.
- Dose delay of nivolumab which results in treatment interruption of > 6 weeks requires treatment discontinuation, with exceptions as noted above.

4.3.5. Nivolumab Infusion Reactions

Since nivolumab contains only human immunoglobulin protein sequences, is unlikely to be immunogenic and induce infusion or hypersensitivity reactions. However, if such a reaction were to occur, it might manifest with fever, chills, rigors, headache, rash, pruritus, arthralgias, hypo- or hypertension, bronchospasm, or other symptoms. All Grade 3 or 4 infusion reactions should be reported within 24 hours as an SAE if criteria are met. Infusion reactions should be graded according to National Institute of cancer (NCI) common terminology criteria for adverse event (CTCAE, Version 4.03) guidelines.

Treatment recommendations are provided below and may be modified based on local treatment standards and guidelines, as appropriate:

For Grade 1 symptoms: (mild reaction; infusion interruption not indicated; intervention not indicated)

- Remain at bedside and monitor subject until recovery from symptoms. The following prophylactic premedications are recommended for future infusions: diphenhydramine 50 mg (or equivalent) and/or acetaminophen 325 to 1000 mg at least 30 minutes before additional nivolumab administrations.

For Grade 2 symptoms: (moderate reaction requires therapy or infusion interruption but responds promptly to symptomatic treatment [eg, antihistamines, non-steroidal anti-inflammatory drugs, narcotics, corticosteroids, bronchodilators, IV fluids]; prophylactic medications indicated for \leq 24 hours)

- Stop the nivolumab infusion, begin an IV infusion of normal saline, and treat the subject with diphenhydramine 50 mg IV (or equivalent) and/or acetaminophen 325 to 1000 mg; remain at bedside and monitor subject until resolution of symptoms. Corticosteroid and/or bronchodilator therapy may also be administered as appropriate. If the infusion is interrupted, then restart the infusion at 50% of the original infusion rate when symptoms resolve; if no further complications ensue after 30 minutes, the rate may be increased to 100% of the original infusion rate. Monitor subject closely. If symptoms recur, then no further nivolumab will be administered at that visit. Administer diphenhydramine 50 mg IV, and remain at bedside and monitor the subject until resolution of symptoms. The amount of study drug infused must be recorded on the electronic case report form (eCRF).
- For future infusions, the following prophylactic premedications are recommended: diphenhydramine 50 mg (or equivalent) and/or acetaminophen 325-1000 mg should be administered >30 minutes before nivolumab infusion. If necessary, corticosteroids (up to 25 mg of SoluCortef or equivalent) may be used.

For Grade 3 or 4 symptoms: (severe reaction, Grade 3: prolonged [ie, not rapidly responsive to symptomatic medication and/or brief interruption of infusion]; recurrence of symptoms following initial improvement; hospitalization indicated for other clinical sequelae [eg, renal impairment, pulmonary infiltrates]. Grade 4: Life threatening; pressor or ventilatory support indicated).

- Immediately discontinue infusion of nivolumab. Begin an IV infusion of normal saline and treat the subject as follows: Recommend bronchodilators, epinephrine 0.2 to 1 mg of a 1:1000 solution for subcutaneous administration or 0.1 to 0.25 mg of a 1:10,000 solution injected slowly for IV administration, and/or diphenhydramine 50 mg IV with methylprednisolone 100 mg IV (or equivalent), as needed. Subject should be monitored until the investigator is comfortable that the symptoms will not recur. Nivolumab will be permanently discontinued. Investigators should follow their institutional guidelines for the treatment of anaphylaxis. Remain at bedside and monitor subject until recovery of the symptoms.

In case of late-occurring hypersensitivity symptoms (eg, appearance of a localized or generalized pruritus within 1 week after treatment), symptomatic treatment may be given (eg, oral antihistamine or corticosteroids).

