3.1.3. Discontinuation Criteria

Patients will be removed from study when any of the following criteria applies:

- Patients with grade 3 or 4 infusion reaction must not receive further treatment with nivolumab

- If radiotherapy is interrupted for > 3 consecutive weeks, patient's protocol treatment will be discontinued.
- Extraordinary Medical Circumstances: If at any time the constraints of this protocol are detrimental to the patient's health, the protocol treatment should be discontinued.
- Patients who develop progressive disease will be discontinued from the protocol therapy.
- Patients who develop unacceptable toxicity will be discontinued from the protocol therapy.
- Patients may withdraw consent and withdraw from the study at any time for any reason.

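### Section 4.3.5 gives two inconsistent consequences for an infusion reaction that recurs after restart: the Grade 2 branch implies continued dosing, while the Grade 3 definition leads to permanent discontinuation

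*Combined protocol and SAP*

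**What the plan says.** Section 4.3.5 asks for infusion reactions to be graded by CTCAE 4.03 and then sets out management by grade.

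- **Grade 2 definition:** "moderate reaction requires therapy or infusion interruption but responds promptly to symptomatic treatment".
- **Grade 2, restart:** "If the infusion is interrupted, then restart the infusion at 50% of the original infusion rate when symptoms resolve".
- **Grade 2, recurrence:** "If symptoms recur, then no further nivolumab will be administered at that visit". Diphenhydramine and observation at the bedside follow.
- **Grade 2, later visits:** "For future infusions, the following prophylactic premedications are recommended: diphenhydramine 50 mg (or equivalent"). This bullet makes no exception for a patient whose symptoms came back after restart.
- **Grade 3 definition:** the criteria include "recurrence of symptoms following initial improvement; hospitalization indicated for other clinical sequelae".
- **Grade 3 or 4, consequence:** "Nivolumab will be permanently discontinued".

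Two other sections carry the same stopping rule. Section 4.3.3 lists, among the reasons for permanent discontinuation, "Any Grade 3 drug-related bronchospasm, hypersensitivity reaction, or infusion reaction, regardless of duration". Section 3.1.3 says "Patients with grade 3 or 4 infusion reaction must not receive further treatment with nivolumab", and the synopsis repeats it under its discontinuation criteria.

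**The concern.** A reaction that settles, is followed by a restart and then returns fits both the recurrence step of the Grade 2 branch and the Grade 3 definition. One route withholds drug for the day and goes on to premedication for future infusions. The other ends nivolumab. No sentence tells a site working in the Grade 2 branch to regrade the recurrence, and none exempts a recurrence after restart from the Grade 3 definition.

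Two things are at stake. The first is whether a patient is re-exposed after a reaction that the protocol's own Grade 3 heading calls severe. The trial runs at three sites, and they could answer differently. The second is the safety data. Section 4.5 lists the CTC grade of adverse events and events leading to permanent treatment discontinuation as safety endpoints, and the incidence of toxicities is a secondary objective (2.2.3). The same event could be entered as Grade 2 without discontinuation or as Grade 3 with it.

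**Working it through.** There is no plan figure to reproduce, because the point turns on wording. The check traces one event through the text and then sizes it with the protocol's own rates.

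**Tracing the event.** Symptoms appear, the infusion is stopped, symptoms resolve, the infusion is restarted at half rate, and symptoms recur.

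| Step | Grade 2 branch of 4.3.5 | Grade 3 definition and stopping rules |
|---|---|---|
| Classification | Recurrence is a step inside Grade 2 | Recurrence after improvement is a Grade 3 criterion (4.3.5) |
| Same visit | No more nivolumab that day | Infusion discontinued at once |
| Later visits | Premedication recommended, no exception for recurrence | No further nivolumab (4.3.5, 4.3.3, 3.1.3, synopsis) |

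The rows agree for the same visit and part company on grade and on later visits. Section 4.3.4 does not settle it: it allows dosing to resume once a drug-related event has resolved to Grade 1 or baseline, and none of its listed exceptions concerns infusion reactions.

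**Inputs for size.**
- Planned numbers: 46, with an estimated maximum of 51 (sections 3 and 8).
- Reaction rates, all grades (section 1.1.4): 1.9% hypersensitivity/infusion reaction in CA209037. In Table 1 for CA209003, infusion-related reactions were 12/306 = 3.9% overall and 3/54 = 5.6% at 3 mg/kg.
- Grade 3-4 infusion-related reactions in Table 1: 0 of 306.
- Total nivolumab doses: 15 (4.3.6).

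**Expected reactions of any grade** = n × rate:
- Low: 46 × 0.019 = 0.87
- High: 51 × 3/54 = 2.83

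**Chance of at least one reaction of any grade** = 1 − (1 − p)^n:
- Low: 1 − 0.981^46 = 0.59
- High: 1 − (51/54)^51 = 0.95

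These are ceilings for the problem, not estimates of it. Section 4.3.5 does not call for interruption in Grade 1, so Grade 1 reactions never reach the restart step. Only Grade 2 reactions that are interrupted, restarted and then recur are affected. The documents give neither the Grade 2 share nor a recurrence rate, so the ceiling cannot be carried down to a count of affected patients.

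**A second bearing from Table 1.** With 0 Grade 3-4 reactions in 306, the one-sided 95% upper bound is 1 − 0.05^(1/306) = 0.0097, and 51 × 0.0097 = 0.5 patients. This bears on the question only if recurrences in CA209003 were coded as Grade 3, and the protocol does not describe that coding.

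**Consequence for one patient.** For a reaction at the first dose, the two routes differ by up to 15 − 1 = 14 further doses. For the safety tables, one patient is 1/51 = 2.0% to 1/46 = 2.2%.

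**The case against.** The best defence is a sequential reading. The recurrence sentence is a bedside instruction. Once the visit is over, the event is graded by CTCAE 4.03, the Grade 3 heading lists recurrence, and the stopping rules apply. On that reading the premedication bullet is meant for Grade 2 reactions that did not recur. Section 4.3.5 also describes its management as recommendations open to local modification, and the last bullet of 4.3.3 requires discontinuation for any event the investigator judges a substantial risk, so nobody is compelled to re-dose.

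Part of this stands. A reader might infer that the protocol expressly keeps such a patient on nivolumab. It does not: continuation is implied by the visit-only wording and the unqualified bullet that follows. It is also fair that investigators keep discretion to stop.

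The sequential reading is nowhere written, however. The recurrence step sits within the Grade 2 branch with its own acute management, and no text sends the reader on to regrade. The local-modification clause covers the treatment recommendations; it does not waive the separate rules in 4.3.3, 3.1.3 and the synopsis, and it leaves more room for sites to differ.

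A reader might also infer that the choice of grade changes the 24-hour report, because 4.3.5 mentions 24 hours for Grade 3 or 4 reactions. The documents do not support this. That sentence applies only if SAE criteria are met, those criteria (5.2) rest on seriousness and not on CTCAE grade, and 5.5 puts every SAE on the same 24-hour clock.

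**Conclusion.** The inconsistency is real and lies within a single section: recurrence after restart is handled inside Grade 2 with continued dosing implied, and is also a criterion for Grade 3, which ends nivolumab under four separate statements. It can lead to different handling of the same patient and inconsistent entries for the descriptive endpoints in 4.5.

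Its size is small. The ceiling is about 0.9 to 2.8 reactions of any grade in 46 to 51 patients, assuming the rates in the two cited nivolumab studies carry over to re-irradiated patients. The affected subset is smaller by an unknown amount. A reader might be tempted to multiply that ceiling by a guessed recurrence rate to get a number of affected patients. The documents offer no such rate, and the all-grade base includes Grade 1 reactions that are not interrupted, so a figure of that kind would not be sound.

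The efficacy analysis is untouched. PFS and OS in section 8 are not defined by treatment discontinuation, and 3.1.4 and 7.5 keep early discontinuers in follow-up. The case for acting rests on the re-exposure question for an individual patient, together with the low cost of the repair.

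**What to change.** In the next amendment the sponsor should reconcile the recurrence sentence and the future-infusions bullet of the Grade 2 branch in 4.3.5 with the Grade 3 definition in that section and with the discontinuation rules in 4.3.3, 3.1.3 and the synopsis, so that one consequence applies to a reaction that resolves, is restarted and recurs. The sentence should carry a cross-reference to those rules and state how the event is graded, consistently with the CTCAE 4.03 instruction already in 4.3.5. Sites should receive the same grading instruction for data entry. Which consequence applies is a clinical decision for the sponsor, and this review does not say which rule is right.

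The cost is a small wording change and cross-references, with no added patients, visits or data.
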